## 10. ADVERSE EVENT REPORTING AND MANAGEMENT

### 10.1 Safety Parameters

Safety parameters will include adverse events, vital signs and clinical laboratory tests.

### 10.2 Adverse Events

An AE is any untoward medical occurrence in a subject or clinical investigation subject administered an investigational product (whether it is the experimental product or the control) and which does not necessarily have a causal relationship with the investigational product. An AE can therefore be any unfavorable and unintended sign, symptom, or disease temporally associated with the use of a medicinal product, whether or not considered related to the medicinal product. Pre-existing events, which increase in frequency or severity or change in nature during or as a consequence of use of a drug in human clinical trials, will also be considered as AEs. AEs may also include pre- or post-treatment complications that occur as a result of protocol-mandated procedures (e.g. invasive procedures such as biopsies).

Any AE (i.e. a new event or an exacerbation of a pre-existing condition) with an onset date after study drug administration up to the last day on study (including the follow-up, off study medication period of the study), should be recorded on the appropriate CRF page(s).

An AE **does not** include:

- medical or surgical procedures (e.g. surgery, endoscopy, tooth extraction, transfusion); the condition that leads to the procedure is an adverse event
- pre-existing diseases or conditions present or detected prior to start of study drug administration, that do not worsen
- situations where an untoward medical occurrence has not occurred (e.g. hospitalization for elective surgery, social and/or convenience admissions)
- overdose of either study drug or concomitant medication without any signs or symptoms unless the subject is hospitalized for observation.

#### 10.2.1 Assessment of AEs

All AEs will be assessed by an investigator and recorded in the subject medical record, including the date of onset and resolution, severity, relationship to study drug, outcome and action taken with study medication. See [Appendix A](#) for details of toxicity grade scales (TGS) relevant to vital signs, gastrointestinal and general system and clinical laboratory adverse events.

For all other reported adverse events, severity should be recorded and graded as:

**Table 9: Severity Grades**

Grade	Severity	Comments
1	Mild	Aware of sign or symptom, but easily tolerated
2	Moderate	Discomfort enough to cause interference with usual activities
3	Severe	Incapacitating with inability to work or perform usual activities
4	Life-threatening	Participant is at immediate risk of death
5	Fatal	Any event causing death

The relationship to study drug therapy should be assessed using the following definitions:

**Table 10: Adverse Event Causality Definitions**

Causality	Comment
Unrelated	AE is clearly due to extraneous causes (e.g. underlying disease, environment, known effect of another drug)
Unlikely	The temporal association between the AE and study drug is such that study drug is not likely to have any reasonable association with the AE
Possible	The AE could have been produced by the subject's clinical state or study drug
Probable	The AE follows a reasonable temporal sequence from the time of study drug administration, abates upon discontinuation of the study drug and cannot be reasonably explained by the known characteristics of the subject's clinical state
Definite	The AE follows a reasonable temporal sequence from the time of study drug administration, abates upon discontinuation of the study drug and/or reappears when study drug is re-introduced

These criteria, in addition to good clinical judgment, should be used as a guide for determining the causal assessment. If it is felt that the event is not related to study drug therapy, then an alternative explanation should be provided.

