### 8.2 Blinding

This is a double blind study. Therefore, subjects, investigational site staff and Sponsor clinical staff will remain blinded to treatment allocation.

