## 12.6 Analysis of Safety

### 12.6.1 Incidence of Adverse events

All AEs will be coded using the Medical Dictionary for Regulatory Activities (MedDRA). AEs will be summarized according to the number of subjects experiencing specific events, reported by system organ class, high level group term, high level term and preferred term. AEs will also be presented by severity and relationship to treatment. All data will be listed.

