8.2 Adverse events

Adverse events will be coded by MedDRA SOC and Preferred Term, and summarised and tabulated for the safety population. For each Preferred Term the number and percent of subjects reporting each adverse event will be tabulated by treatment group. These tables include:

- Adverse event summary table
- Adverse events occurring prior to study treatment, if any
- All treatment-emergent adverse events
- Most common (>5%) treatment-emergent adverse events in any group
- Treatment emergent adverse events that were possibly, probably or definitely related to the study medication (if large study then only the most common of these may be presented in Section 12 tables)
- Severe adverse events
- Adverse events causing withdrawal
- All adverse events by maximum severity and relationship to study treatment, with subject identification. (ICH format)

Odds ratios will be calculated for the 15 most commonly reported Preferred Terms.

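### In Protocol Table 10 the Definite causality grade is easier to meet than Probable, so in displays by relationship level it is not reliably the stronger grade

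*Protocol*

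**What the plan says.** Protocol Section 10.2.1 has the investigator record each adverse event's relationship to study drug, and the sentence that introduces Table 10 says the definitions there should be used. The two top rows are:

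- **Probable**: a reasonable temporal sequence from dosing, and the event "abates upon discontinuation of the study drug and cannot be reasonably explained by the known characteristics of the subject's clinical state".
- **Definite**: the same requirement on timing, and the event "abates upon discontinuation of the study drug and/or reappears when study drug is re-introduced".

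Lower on the scale, Possible covers an event that either the clinical state or the drug could have produced, and Unrelated covers an event with a clear outside cause, underlying disease being one of the examples. Below the table the protocol adds: "These criteria, in addition to good clinical judgment, should be used as a guide for determining the causal assessment".

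The grades are used in reporting. Protocol Section 12.6.1 says "AEs will also be presented by severity and relationship to treatment". SAP Section 8.2 lists "All adverse events by maximum severity and relationship to study treatment, with subject identification", and the SAP's table list repeats that display for treatment-emergent events. SAP Section 8.2 also has a separate table that pools possibly, probably and definitely related events.

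**The concern.** A causality scale should become stricter as it rises. Here the top row drops one of the conditions of the row below and adds nothing compulsory in its place. Reappearance on re-introduction would normally set Definite apart, but it is only one of two alternatives.

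What is at stake is the reading of any table or narrative that separates Definite from Probable. A reader will take Definite as the strongest evidence of a drug effect. As worded, it can include events that the subject's disease could equally explain and that cleared after dosing stopped. Under Protocol Section 8.2, "subjects, investigational site staff and Sponsor clinical staff will remain blinded to treatment allocation", so the same wording applies to placebo subjects.

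**Working it through.** The plan gives no figure to reproduce. The check is a logical comparison of the two rows.

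**Criteria, all from Table 10**

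| Criterion | Probable | Definite |
|---|---|---|
| T: reasonable temporal sequence | required | required |
| D: abates on stopping | required | D or R is enough |
| R: reappears on re-introduction | not mentioned | D or R is enough |
| N: not reasonably explained by the clinical state | required | not mentioned |

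As formulas: Probable = T and D and N. Definite = T and (D or R).

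**Nesting.** If T, D and N all hold, then T and D hold, so Definite holds. Every Probable event is therefore a Definite event.

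**Enumeration.** Four yes/no criteria give 2 × 2 × 2 × 2 = 16 combinations.

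- Probable fixes T, D and N and leaves R free: 2 combinations.
- Definite fixes T, allows three of the four D/R pairs and leaves N free: 3 × 2 = 6 combinations.
- Probable but not Definite: 0. Definite but not Probable: 6 − 2 = 4.

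These counts show the direction of the nesting. They are not frequencies. Two of the four extra combinations have the event reappearing without having abated, which is barely coherent. A third is a positive rechallenge, where a high grade can be defended. The fourth carries the point: T yes, D yes, R no, N no. Such an event meets Possible, fails Probable and meets Definite.

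**Other readings of the and/or**

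- (T and D) or R: the 8 combinations with R, plus 2 with T and D but no R, make 10. Probable is still wholly contained.
- Strictly T and D and R: 2 combinations. The nesting disappears, but this is not what the row says, and N is still missing, so a rechallenged event that the clinical state explains would meet Definite and fail Probable.

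**Corrected row.** T and D and N and R gives 1 combination, and it lies inside Probable. The order is restored.

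**Where the split is used**

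- By-relationship displays (Protocol Section 12.6.1, SAP Section 8.2, SAP table list): affected.
- Pooled related-event table (SAP Section 8.2): Possible, Probable and Definite count alike, so it is unaffected.
- Primary safety endpoint (Protocol Section 4.2): incidence and severity of adverse events, with vital signs and laboratory changes. Causality level is not part of it.
- Late event reporting (Protocol Section 10.2.2), regulatory reporting (Section 10.3.4) and the causality-based parts of the discontinuation guidance (Section 10.6): all are set at a possible relationship or higher, so none depends on the Probable/Definite boundary.

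**The case against.** The strongest reply is that two rows are being read mechanically out of a five-level scale. The protocol calls the criteria a guide to be used with clinical judgment. Events with a clear outside cause already have a home in Unrelated, and events that disease or drug could have caused have one in Possible. A sensible investigator would not grade such an event Definite. Nothing that triggers action depends on the split, no test of Probable against Definite is planned, and any inflation would affect all arms.

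Much of this stands, and it limits the reach of the point. It does not remove the defect. Unrelated applies only when the outside cause is clear, so events merely explainable by the clinical state stay open to Definite. If judgment has to override the top row to put the scale back in order, the row is not doing its work.

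Several stronger readings are tempting and are not supported:

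- A reader might infer that any event after dosing that clears once drug stops becomes Definite. The row still requires a reasonable temporal sequence.
- A reader might infer that every event ongoing at Week 24 and gone by the Week 28 visit (Protocol Section 7.2.10) will be graded Definite. Stopping drug does supply the dechallenge, but no section tells sites to re-grade events on that ground.
- A reader might infer that grading will be arbitrary across the roughly 30 sites, or that Definite counts mean nothing. The documents give no data on rater agreement, and the by-arm comparison with placebo remains available.

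**Conclusion.** The point holds in limited form. As written, Definite is strictly easier to meet than Probable, under both the natural reading of the row and the looser one. In the by-relationship displays a Definite grade is therefore not reliably stronger evidence than a Probable grade, in any arm.

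The number of events affected cannot be derived from the documents. The conclusion that the pooled table is untouched assumes that each affected event would properly be at least Possible, which is the natural grade for a temporally plausible event that either the clinical state or the drug could explain. A reader might also take the defect to undermine the primary safety endpoint, because adverse events are part of it. The documents do not support that, since the endpoint counts events by incidence and severity without regard to attribution. The wording is worth correcting because the correction is specific and cheap.

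**What to change.** Reconcile the two rows of Table 10. Definite should require every Probable criterion, including no reasonable explanation by the clinical state, plus reappearance where study drug happened to be re-introduced. An event not followed by re-introduction would then be graded no higher than Probable. This is a grading definition only; it does not call for rechallenging anyone.

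If events have already been graded under the current text, make the SAP's pooled table of possibly, probably and definitely related events the main relationship display, and state the limitation beside any table that shows the levels separately. Pooling only Probable with Definite is not enough, because events that belonged in Possible would stay in the combined class.

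The cost is a wording change to Table 10 and to any matching case report form guidance, and fewer events will be called Definite. Doses, visits, sample size and efficacy analyses do not change.

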#### 10.2.2 Adverse Event Reporting Period

All adverse events, regardless of severity, causality or seriousness must be reported from the date of informed consent until 28 days after the last dose of study medication. However, any adverse event that the investigator believes is at least possibly related to study medication should be reported regardless of time elapsed from the final dose.

### 10.3 Serious Adverse Events

#### 10.3.1 Serious Adverse Event Definition

A serious adverse event (SAE) is defined as follows:

Any adverse drug experience occurring at any dose that results in any of the following outcomes:

- death
- life-threatening situation (subject is at immediate risk of death)
- inpatient hospitalization or prolongation of existing hospitalization (excluding those for study therapy or placement of an indwelling catheter, unless associated with other serious events)
- persistent or significant disability/incapacity
- congenital anomaly/birth defect in the offspring of a subject who received study drug
- other: Important medical events that may not result in death, be immediately life-threatening, or require hospitalization, may be considered a SAE when, based upon appropriate medical judgment, they may jeopardize the subject and may require medical or surgical intervention to prevent one of the outcomes listed in this definition. Examples of such events are:
  - intensive treatment in an emergency room or at home for allergic bronchospasm
  - blood dyscrasias or convulsions that do not result in hospitalization
  - development of drug dependency or drug abuse

#### 10.3.2 Clarification of Serious Adverse Events

Death is an outcome of an AE, and not an AE in itself. In reports of death due to "Disease Progression", where no other information is provided, the death will be assumed to have resulted from progression of the disease being treated with the study drug.

All deaths, regardless of cause, must be reported to Immuron for subjects on study and within 28 days of last administration of study drug.

“Occurring at any dose” does not imply that the subject is receiving study drug at the time of the event. Dosing may have been given as treatment cycles or interrupted temporarily prior to the onset of the SAE, but may have contributed to the event.

“Life-threatening” means that the subject was at immediate risk of death from the event as it occurred. This does not include an event that might have led to death, if it had occurred with greater severity.

Complications that occur during hospitalizations are AEs. If a complication prolongs hospitalization, it is a SAE.

“In-patient hospitalization” means the subject has been formally admitted to a hospital for medical reasons, for any length of time. This may or may not be overnight. It does not include presentation and care within an emergency department.

The investigator should attempt to establish a diagnosis of the event based on signs, symptoms and/or other clinical information. When available, a diagnosis should be documented as the AE and/or SAE and not the individual signs/symptoms.

### 10.3.3 Serious Adverse Event Reporting Requirements

Immuron has requirements for expedited reporting of SAE’s that meet specific criteria to worldwide regulatory authorities; therefore, all appropriate parties must be notified immediately of any SAE that occurs after the first dose of study drug has been administered. The procedures for reporting all SAEs, regardless of causal relationship, are as follows:

- Complete the “Serious Adverse Event Report” CRF page
- Send the SAE report to the Sponsor SAE hotline within 24 hours of the investigator’s knowledge of the event:

**[contact]  
**[contact]  
**Email:** [contact]

- For fatal or life-threatening events, also send copies of hospital case reports, autopsy reports, and other documents when requested and applicable

Immuron may request additional information from the investigator to ensure the timely completion of accurate safety reports.

The investigator must take all therapeutic measures necessary for resolution of the SAE. Any medications necessary for treatment of the SAE must be recorded in the concomitant medication section of the subject’s CRF.

### 10.3.4 Investigator Reporting Requirements for SAEs

A SAE may qualify for reporting to regulatory authorities if the SAE is considered to have a possible causal relationship to the study drug and is unexpected/unlisted based upon the current Investigator’s Brochure. In this case, all investigators will receive a formal notification describing the SAE.

Where this is required by local regulatory authorities, and in accordance with the local institutional policy, the investigator should notify (in writing) the Institutional Review Board (IRB)/Ethics Committee (IEC) of SAEs according to local timelines.

#### 10.4 Follow up of Serious and Non-serious Adverse Events

Follow-up of SAEs and non-serious AEs will continue through the last day on study (including follow-up) until the investigator and/or Immuron determine that the subject's condition is stable, whichever is longer. Immuron may request that all clinically significant AEs be followed until resolution or for a period of 30 days after.

#### 10.5 Clinical Laboratory Abnormalities and Other Abnormal Assessments as AEs or SAEs

All laboratory values must be reviewed by the investigator. Given that all laboratory data are collected and statistically analyzed with respect to relevant reference ranges, laboratory abnormalities that occur without related clinical symptoms and signs should generally not be recorded as adverse events unless they represent a clinically significant event. Where possible, the overall diagnosis rather than the laboratory abnormality should be recorded as the AE. This will avoid duplication of laboratory abnormalities in both the AE and laboratory reports.

Any laboratory test result that meets the criteria for a SAE (refer to [Section 10.3.1](#)) should be recorded as an AE, the AE page of the CRF completed and a SAE form also completed in order for the sponsor to collect additional information about that abnormality, including information regarding relationship to study product or other causes, any action taken and resolution.

#### 10.6 Guidance for Discontinuation of Treatment

To date, no specific toxicities have been identified that result from IMM-124E treatment. Any toxicities and/or abnormal laboratory findings should be investigated for etiology and graded according to Table 8 ([Section 10.2.1](#)) and [Appendix A](#).

The following toxicity management will be followed:

**Grade 1 or 2:** Patients may continue study drug.

**Grade 3:** Patients with any Grade 3 toxicity considered to be at least possibly related to treatment (i.e. treatment related events) should be evaluated carefully by the investigator prior to continuing study drug. Investigators may discuss individual cases with the Medical Monitor.

**Grade 4:** Patients developing any Grade 4 toxicity should have treatment interrupted, unless the Grade 4 toxicity is clearly unrelated to study drug and continued treatment does not pose a serious risk to the patient. After the event has returned to normal or baseline levels, study drug may be re-started. If the toxicity re-appears, the investigator should contact the Medical Monitor to discuss the subject's withdrawal.

For any subject experiencing any event (irrespective of severity) which, in the opinion of the Investigator, contraindicates further dosing in that subject and the event is considered to be at least possibly related to treatment (or where causality to study treatment cannot be ruled out – see [Section 10.2.1](#)), continued dosing of the subject should be interrupted. In all cases, the final treatment decisions, made in response to toxicity, are the responsibility of the Principal Investigator. A careful evaluation of the potential risk/benefit will dictate the optimal therapeutic course. Should treatment be interrupted, re-initiation will follow review of the available safety data and in agreement with the Sponsor. There will be no dose reduction or modification.

If the investigator deems that management of the patient's medical condition requires knowledge of the study treatment regimen, then the Medical Monitor must be contacted for consultation and the procedures described in [Section 8.2](#) followed. If a patient dies from an event that is considered to be at least possibly related to treatment, continued dosing of all study participants should be interrupted:

Clinically significant suspected adverse drug reactions, and serious adverse events considered to be related to study procedures will be followed until resolved or considered stable. All subjects who experience a study drug related AE should be followed until resolution of the AE, even if the subject has discontinued study drug.

If an unscheduled interruption of study drug occurs, the study site should notify the sponsor at the earliest possible time. A missed dose will not be made up. In the event that a subject requires an unscheduled interruption of study drug under conditions other than those associated with toxicity, the case will be reviewed by the Sponsor to determine whether such a subject will be allowed to resume study drug.

Subjects withdrawn from study drug will be treated as deemed appropriate by the investigator. Follow-up procedures should be performed and the appropriate CRFs should be completed.

### **10.7 Warnings and Precautions**

The adverse event profile in humans is IMM-124E has not been fully characterized. In clinical trials and commercial use at doses equal or lower than those used in this study, IMM-124E was well tolerated with a safety profile expected of bovine colostrum. The most common adverse reactions expected include modified bowel movements and nausea.

For further information regarding warnings and precautions with the study drug, please refer to the Investigator's Brochure for Imm-124E.

